## **1. BACKGROUND AND RATIONALE**

### **1.1 Background**

Approximately 4% of the American population suffers from food allergy [1]. More specifically, over 3 million Americans are affected by an allergy to peanuts, tree nuts, or both, and the prevalence has continued to rise over the past decade particularly in the pediatric population [2]. In addition, peanut allergy is the leading cause of fatal allergic reactions in the United States [3, 4]. Currently, the standard of care for peanut allergy is a strict avoidance of peanut and ready-access to self-injectable epinephrine; however, implementation of an avoidance diet is complex and accidental ingestions are common. In one report, up to 50% of food-allergic patients had an allergic reaction during a two-year period [5]. More recent data shows that the annual incidence rate for food allergic reactions following accidental exposure is ~15% for children with peanut allergy [6]. Since only 20% of peanut allergy is estimated to be naturally outgrown, the majority of patients face a life-long risk of anaphylaxis and death [7, 8].

### **1.2 Rationale**

Traditional subcutaneous immunotherapy is useful in treating forms of inhalant and venom allergies but has proven unsafe in treating food allergy [9, 10]. Oral immunotherapy (OIT) has been reported by the [name] research group and others to result in protection from anaphylaxis to a variety of food proteins [11-19]. In a recent open-label peanut OIT trial by Jones et al., 27 of 29 subjects receiving a daily maintenance dose successfully passed an open food challenge to 3900 mg of peanut protein. This and other ongoing studies by the [name] group have demonstrated that OIT induces clinical desensitization to peanut, with humoral and cellular changes suggestive of the development of long-term tolerance [12]. Furthermore, peanut OIT appears to be safe in children with peanut allergy treated in a controlled setting by trained personnel [20].

Sublingual immunotherapy (SLIT) has also been proposed as a safe, alternative form of immunotherapy to reduce clinical reaction rates during oral food challenge for adults with hazelnut [21] or kiwi allergy [22]. [name] research team has shown that 12 months of peanut SLIT is able to induce an increase in reaction threshold while receiving the SLIT study drug, i.e., clinical desensitization [23]. While clinical desensitization is demonstrated in almost all OIT and SLIT studies for food allergy, tolerance, which refers to a non-reactive state of the immune system that persists after discontinuation of peanut study drug, has only rarely been tested and requires further study. Recent data presented by [name] research team since the onset of this trial has shown that basophils return to their reactive state after the discontinuation of immunotherapy ([24]). This suggests that the effect of OIT and SLIT may be transient with the development of true immunological tolerance only a rare occurrence. On this background, the term sustained unresponsiveness (SU) was coined ([25]) to refer to the phenomenon of a non-reactive state that persists after discontinuation of therapy but wanes after a period of time.

Various studies of OIT and SLIT have looked at SU but these studies have been small and

heterogeneous making it difficult to make generalizations [17, 26, 27]. The loss of SU and the desensitization effect has not yet been studied in a systematic fashion within a single population. With the FDA approval of food immunotherapy potentially on the horizon, practical questions have arisen including questions about the frequency of dosing and the response to missed doses due to illness, non-compliance, or other factors. We hope that an understanding of the characteristics of SU will provide important clinical data in anticipation of the broader use of immunotherapy for food allergy while giving further insights into the immune mechanisms of desensitization, SU, and the loss of SU.

### **1.3 Rationale for Selection of Study Population**

We will enroll subjects between 1 and 11 years who have a history of clinical allergy to peanut or serologic evidence of allergic sensitization with a specific IgE > 0.35 kU/L to peanut. The age group for study was selected based on our ongoing peanut SLIT trial (NCT# 00597727; UNC IRB 11-2296; Duke Pro00001553) which has demonstrated successful desensitization to peanut in this age group.

### **1.4 Known and Potential Risks and Benefits to Human Participants**

#### **1.4.1 Risks**

The build-up and daily maintenance doses of SLIT may cause allergic symptoms including sneezing, rhinorrhea, urticaria, angioedema, flushing, flares of eczema, ocular, nasal, oral and/or throat pruritus, throat tightness, nausea, vomiting, abdominal discomfort, cough, wheezing, and/or shortness of breath in addition to severe anaphylaxis. The most common symptom associated with SLIT dosing is oropharyngeal itching present in 9.3% of all doses. As of October 24, 2012, no subject in our ongoing SLIT study (NCT# 00597727; UNC IRB 11-2296; Duke Pro00001553) has had dosing-related anaphylaxis requiring treatment with epinephrine [23]. The likelihood of a subject experiencing allergic symptoms will be lessened by starting at small amounts of the peanut protein for dosing per this SLIT protocol.

Double-blind, placebo-controlled food challenges (DBPCFC) may induce an allergic response with symptoms similar to those described for SLIT dosing. The risk of a severe allergic reaction is reduced by conducting the challenge in a monitored clinic setting, initiating the challenge with a very small amount of the food, gradually increasing the dose, and stopping the challenge at the first sign of a reaction. If subjects have an allergic reaction during the challenges, they may need oral, intramuscular, or intravenous medications (subjects will have an IV catheter in place during all DBPCFCs). Trained personnel, including a physician, as well as medications and equipment, will be immediately available to treat any reaction.

Other risks include those related to blood drawing and skin testing. Blood drawing may aggravate a pre-existing anemic condition, but this risk is minimized by restricting the volume drawn to a maximum of 3 ml per kg in accordance with United States Department of Health and Human Services recommendations [28]. Additional risks are those attendant to any needle puncture, including slight bruising, local infection, or the possibility of the subject fainting.

Skin prick tests (not intradermal) will be performed by techniques reflecting general standard of care and cause discomfort (the sensation of a scratch and a pruritic, transient hive may result). Such tests could theoretically induce a systemic allergic reaction, but this is exceedingly rare.

#### **1.4.2 Benefits**

The immediate benefits for the subject include the possibility of a decrease in clinical reactivity to peanut and diminished allergic reaction following an accidental ingestion of peanut, as well as the possibility of altering the natural course of the peanut allergy. Additionally, subjects may develop lasting desensitization to peanut off of therapy, which is otherwise not likely to happen. Should persistence of desensitization occur, subjects could have the ability to broaden their diet and experience an improved quality of life with less of the restrictions imposed by a life-threatening food allergy. This study will also help to expand the knowledge of food allergy in general and may lead to new management and therapeutic protocols for individuals with other food allergies.

## **2. OBJECTIVES**

### **2.1 Primary and Secondary Objectives**

Our *central hypothesis* is that peanut SLIT will induce clinical desensitization after at least 48 months of peanut SLIT that will persist for a period of time after the discontinuation of therapy. We will address our hypothesis through investigations focused on the following *objectives*:

#### ***Primary Objective:***

First, we aim to estimate the population sensitization threshold, the dose predicted to provoke reactions in X% of the peanut-allergic population after at least 48 months of peanut SLIT treatment. Second, given the above estimated population sensitization threshold and the administered dose levels that it lies between, we would like to characterize the SU curve with respect to time for several end points including time for desensitization threshold as assessed by the final DBPCFC to reduce by half of the estimated sensitization threshold, to drop by a level of the administered dose level, to remain above minimal clinically relevant threshold (MCRT) and finally, to maintain threshold constancy.

#### ***Purpose and expectations:***

This two-part primary objective is designed to estimate the level of desensitization induced by peanut SLIT through determination of the population sensitization threshold and to characterize its potential for SU by calculation of a desensitization decay curve. We expect to demonstrate successful desensitization above the MCRT (300 mg peanut protein) for the population and to demonstrate SU for a period of time between 1 and 17 weeks after discontinuation of peanut SLIT therapy.

The studies under the Primary Objective will determine the level of protection against accidental ingestions of peanut provided by peanut SLIT therapy. These results will further determine whether peanut SLIT can be considered a viable option alongside OIT and EPIT for peanut allergy. In addition, the studies will provide data regarding the duration of the desensitization effect which may have important clinical ramifications on the optimal dosing interval and the effect of missed doses/non-compliance. These results could also shed further insight into the immune mechanisms involved in the development and loss of desensitization.

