### **5.9 Study Randomization Procedures**

The peanut SLIT treatment is open-label for the duration of the study. At the time of the 48 month desensitization DBPCFC, subjects will be randomly assigned an interval from 1 to 17 weeks during which peanut SLIT study drug and all other peanut will be strictly avoided. All DBPCFCs are conducted in a double-blind manner. All randomization is performed using a randomization scheme provided by our biostatistician collaborators performed by representatives in [name] laboratory and laboratory personnel are unblinded throughout the study.

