1. BACKGROUND

This Statistical Analysis Plan (SAP) has been written to address the concerns identified in the March 19, 2014 protocol abbreviated Peanut SLIT and Tolerance (UNC IRB#11-2308), which included our proposed primary analysis plan aimed at assessing effectiveness of peanut SLIT to induce clinical tolerance 6 months after its discontinuation.

We recognize the investigating team's concerns regarding the assumption that patients will be able to clear the food challenge administered after 6 months of SLIT discontinuation to demonstrate clinical tolerance. The team believes this assumption is rather optimistic, less supported by prior research and suspects that the current study protocol calls for negligible success rate by the end of 6 months of SLIT discontinuation as most of the subjects would fail for clinical tolerance. Since time to loss of desensitization (TLD) is an important dimension that, in our knowledge, no prior study has investigated, provides clinically valuable information and helps facilitate future study design, this study provides an opportunity and a robust framework to study the same. As a result, the revised protocol analyzes a systematic approach to address this concern. We believe that with few changes in the study design and efficacy analysis plan, the revised protocol will help address new objectives of primary enquiry and will provide greater precision to cater to individual's need.

With 51 total enrollees, we are midway through the study's conduct with 24 subjects clearing 48 months of dose maintenance period and waiting to be administered the 48th month food challenge and to be randomized to the placebo or the treatment arm as per the existing protocol. The revised study design calls for amendments beyond the 48 months' period of dose maintenance to include 48th month food challenge followed by discontinuation of SLIT for all subjects for at most 17 weeks, dissolving the need for a two-arm trial. Subjects will be randomized to weekly observed time points during 17 weeks following the 48th month food challenge when the final food challenge will be administered to assess individual's persistent desensitization also known as sustained unresponsiveness (SU). The structure of this final food challenge will be similar to that of the earlier (48th month) food challenge with similar levels of administered drug doses.

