10. EFFICACY ANALYSES

10.1 Primary Efficacy Analysis Approach

To begin with, our primary analysis will comprise of two parts.

First, an Interval-Censoring Survival Analysis (ICSA) approach will be used to analyze the 48th month DBPCFC threshold data (Collett, 1993, Chapter 9, Taylor et al - 2009). The methodology is appropriate when the exact dose that provokes a reaction in an individual is not known but it is known to fall into a particular interval. Using ICSA, if an individual had an objective reaction at the first dose in a challenge trial, then left-censoring occurred, and the NOAEL was set to zero with the LOAEL set as that first dose. If an individual did not experience an objective reaction after the largest challenge dose, then right-censoring occurred, and the NOAEL was set to that largest challenge dose (if a subjective response occurred at that largest dose, this was also considered as the objective NOAEL), while the LOAEL was set to infinity. In all other cases, interval-censoring occurs bounded by the NOAEL and LOAEL. Parametric (Log-normal, Weibull) and non-parametric dose-distribution model will be used to estimate the ED10 and the ED05, the doses predicted to provoke reactions in 10% and 5%, respectively, of the peanut-allergic population.

Second, for each dose interval bounded by the NOAEL and LOAEL of the 48th month DBPCFC, we will conduct survival analysis with case-1 censoring (Huang – Wellner lecture notes, Kosorok et al, 1998) to estimate time to loss of desensitization. We will assume exponential

distribution with log link for the decay of sensitivity threshold for those who take the final challenge. This assumption of exponential decay will be validated using semi/non-parametric analysis with an option for modeling with a more flexible **semi-parametric** distribution. The analyses will be performed with and without the effect of baseline and other clinical covariates. This analysis will provide an initial insight into effectiveness of peanut SLIT in longevity of induced clinical desensitization and SU.

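### The plan attributes month-48 thresholds and their persistence to SLIT, but no comparison separates SLIT from natural resolution, which matters most for the sustained-unresponsiveness curve

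*Protocol*

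**What the plan says.** The protocol's central hypothesis (2.1) is that "peanut SLIT will induce clinical desensitization after at least 48 months of peanut SLIT". The purpose statement under the primary objective calls the two-part objective "designed to estimate the level of desensitization induced by peanut SLIT" and continues: "The studies under the Primary Objective will determine the level of protection against accidental ingestions of peanut provided by peanut SLIT therapy". SAP 10.1 closes its description of the time-to-loss analysis with: "This analysis will provide an initial insight into effectiveness of peanut SLIT in longevity of induced clinical desensitization and SU".

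On the design, Protocol 5.9 states: "The peanut SLIT treatment is open-label for the duration of the study". What is randomized is the avoidance period after the month-48 challenge: "subjects will be randomly assigned an interval from 1 to 17 weeks". SAP section 1 describes the amendment, under which all children stop SLIT after the month-48 challenge, as "dissolving the need for a two-arm trial".

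On natural history, Protocol 1.1 says: "Since only 20% of peanut allergy is estimated to be naturally outgrown". It gives no age range and no period. Protocol 1.4.2 regards lasting desensitization off therapy as otherwise unlikely, also without a rate. Neither document returns to natural resolution in the analysis.

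**The concern.** The wording is causal: the threshold reached at month 48, and its survival after stopping, are credited to SLIT. To support that, the plan would need some account of what these children would have tolerated after four or more years without SLIT. It has none. The entry challenge confirms allergy at baseline, but it cannot tell a child who later outgrew the allergy from a child whom SLIT desensitized.

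A child who outgrew the allergy would exceed 300 mg at month 48, enter the avoidance phase, and be expected to meet the definition of sustained unresponsiveness in SAP section 4. That child would count in favour of SLIT in both parts of the analysis. The protocol intends the duration results to inform dosing intervals and the consequences of missed doses, so an overstated persistence would carry into those uses.

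**Working it through.** **1. Claim against design.**

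| Conclusion in the plan | What the design supplies |
|---|---|
| Desensitization induced by SLIT (Protocol 2.1) | Month-48 thresholds in children who all took SLIT |
| Protection provided by SLIT (Protocol 2.1) | The same thresholds, with no untreated or external reference |
| Effectiveness of SLIT in longevity (SAP 10.1) | Loss by randomized week, in children who all took SLIT and all stopped |

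Randomizing the week makes the observation time independent of the time to loss. It says nothing about why a child has not lost tolerance.

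**2. The plan's own sample size.** Protocol 8.1.1 gives 50, from 50% versus 90% pass rates, 2:1 placebo to continued SLIT, 80% power, two-sided 0.05 and 10% dropout. With pooled rate (0.9 + 2 × 0.5)/3 = 0.633:

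n(SLIT) = [1.96 √(1.5 × 0.633 × 0.367) + 0.842 √(0.09 + 0.25/2)]² / 0.4² = (1.157 + 0.390)² / 0.16 = 15.0

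This gives 15 + 30 = 45, and 45/0.9 = 50. The figure reproduces. It belongs to a randomization that would have followed the 48 months of SLIT, so it neither sizes nor supplies an untreated comparison over that period.

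**3. The loss model.** SAP 10.1 has a probability mass for loss at time zero and, for all other children, F(t) = 1 − exp(−λt). F(t) tends to 1, so every challenged child is modelled as eventually losing desensitization. There is no mass for never.

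**4. Illustration of the effect on time to loss.** The documents give neither a 48-month resolution rate nor an expected time to loss, so both are assumptions here. Let r be the never-lose share among children entering avoidance and h the median time to loss in the rest. *Median time to loss* here is the half-life of the loss curve, not the threshold half-life listed as an endpoint. The true retained share is

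S(t) = r + (1 − r) × 0.5^(t/h).

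The SAP's exponential is fitted to expected data, weeks 1 to 17 equally weighted, by maximizing over λ

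Σ { S(t)(−λt) + [1 − S(t)] ln(1 − e^(−λt)) },

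and the fitted median is ln 2/λ. Covariates and month-48 dose strata are ignored.

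| Assumed true median (weeks) | r = 0% | 5% | 10% | 20% |
|---|---|---|---|---|
| 4 | 4.0 | 4.6 | 5.2 | 6.7 |
| 8 | 8.0 | 8.7 | 9.5 | 11.3 |
| 26 | 26.0 | 27.6 | 29.4 | 33.6 |

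At r = 10% the fitted median is too long by 30% (5.2/4), 19% (9.5/8) and 13% (29.4/26). The retained share at week 17 moves the same way. For h = 8, 0.5^(17/8) = 0.229, which becomes 0.1 + 0.9 × 0.229 = 0.306 at r = 10% and 0.2 + 0.8 × 0.229 = 0.383 at r = 20%. At r = 20% it is 24% instead of 5% for h = 4, and 71% instead of 64% for h = 26.

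**5. Effect on ED05 and ED10.** Assume log-normal thresholds with log-SD σ, and a share r of the challenged children who do not react. The ED for proportion p is then multiplied by exp{σ[z(p/(1 − r)) − z(p)]}. For σ from 1.0 to 1.5 (assumed), ED05 and ED10 rise by about 3–5% at r = 5% and 12–22% at r = 20%. Lower-tail doses move less, because children who do not react sit in the upper tail.

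**The case against.** The strongest reply is that the listed endpoints make no causal comparison. ED05, ED10, time to loss and proportions at a fixed time are estimates in treated children, and the primary objective itself speaks of thresholds after at least 48 months of treatment. The contested sentence is narrative, a hypothesis may be worded causally, and the SAP claims only an initial insight. The trial is an open-label phase I/II study amended with 51 children enrolled, when a concurrent control was no longer available. This stands for the estimates. It does not cover a statement that the studies will determine the protection SLIT provides.

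The second reply concerns the model. SAP 10.1 plans to check the exponential with semi- or non-parametric methods, and SAP 8.1 plans non-parametric curves over the 17 weeks. Those curves do not force loss and can show a plateau. This also stands, so the restriction applies to the parametric model only. A plateau would still not reveal whether it reflects SLIT or outgrown allergy.

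Three stronger readings are tempting and not supported:

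- A reader might apply the 20% to this cohort, either as a count of children who would have passed anyway or as a benchmark for the share tolerating 5000 mg. The figure has no time window and concerns peanut allergy in general, whereas these children were challenge-positive at entry. It is not a 48-month rate.
- A reader might infer material favourable bias in both primary parts. The listed part-one endpoints are lower-tail doses, and their shift is small unless the share is large.
- A reader might think the amendment removed the needed control. The superseded placebo arm would have started only after the SLIT period.

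**Conclusion.** The point holds as one of attribution. The design can describe thresholds and persistence in children treated for at least 48 months. It cannot assign them to SLIT, and both documents say or imply that it will. The listed estimates need not be discarded.

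The part most exposed is the sustained-unresponsiveness curve under the exponential model, where any never-lose share lengthens the apparent time to loss. The actual size cannot be derived from the documents. Across the assumed medians of 4 to 26 weeks and shares of 5% to 20%, the fitted median is too long by about 6% (27.6/26) to 68% (6.7/4) as a description of the children who do lose tolerance. If the never-lose children are counted in, the observed retained proportion is still a correct description of the whole cohort; only its explanation is open.

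**What to change.** 1. In the purpose statement of Protocol 2.1 and in SAP 10.1, restate the conclusions as thresholds and persistence observed after at least 48 months of SLIT. Add a sentence that natural resolution is not separated from an effect of SLIT. The hypothesis in Protocol 2.1 can stay as a hypothesis.

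2. In SAP 10.1, prespecify a sensitivity fit of the exponential loss model with a never-lose share fixed over an assumed range, for example 0%, 5%, 10% and 20%: F(t) = (1 − r)(1 − e^(−λt)) for children who enter avoidance. Report it as showing how far the estimated median time to loss depends on that share. Do not present it as separating natural history from SLIT: a child who outgrew the allergy and a child with durable SLIT-induced tolerance look the same in these data.

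The cost is a change of wording and one additional fit on data already planned, with no new arm, visit or child. The downside is a more modest claim.
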